5.1.3 Electronic patient records

The clinical data will be collected from the medical charts using a case report form. Each patient will be assigned a unique study code, as described in chapter 8. A copy of the CRF will be sent to the coordinating centre (Leiden University Medical Centre) for data entry and a copy will be kept at the original centre. We will obtain the following information from electronic patient records, along with the dates at which measurements were performed:

• Variables that will be extracted from the electronic patient records:

General

- Year of birth
- Vital status, if deceased:
 - Cause of death
- Type of haemophilia
- Bodyweight and height
- Age at first joint bleed
- F8 or F9 genotype
- Date of first blood sample
- Date of last FVIII/FIX infusion before first blood sample
- Product and dose used during last FVIII/FIX infusion before first blood sample
- Baseline FVIII/FIX activity level (one-stage clotting assay/chromogenic assay)
- Baseline FVIII/FIX antigen level
- Baseline VWF activity level, baseline VWF antigen level (VWF: Ag)
- Current treatment type (prophylactic treatment or on-demand treatment) , frequency and dose
- Bodyweight and height

Current treatment

- Current treatment regimen
 - Current product(s) used
 - Prophylaxis vs. on-demand treatment

- Frequency, dose of prophylactic treatment (if applicable)
- Frequency, dose of treatment for minor/major/life-threatening bleeding
- Immune tolerance induction protocol (if applicable)
 - Current product(s) used
 - Frequency, dose
 - o Use of immune modulatory medication

Co-morbidities

- HIV status, if positive:
 - o Treatment type
 - HIV viral load
- Current and previous hepatitis C status, if positive:
 - HCV genotype
 - o Date of last positive HCV RNA assay
 - Outcome of last Fibroscan
 - Latest Child-Pugh score
 - o Presence of ascites
 - Presence of bleeding oesophageal varices
 - Presence of hepatic encephalopathy
 - Liver transplantation
 - o All previous HCV treatment regiments
 - o SVR after last HCV treatment

Inhibitor development

- Number of exposure days to FVIII (<50 EDs, 51-100 EDs, 101-150 EDs, >150 EDs)
- Previous or current Bethesda assay, if positive:
 - o Number of exposure days to FVIII before first positive inhibitor assay
 - First two positive inhibitor assays (date, inhibitor titre and FVIII:C recovery)
 - o Peak inhibitor titre and corresponding FVIII:C recovery
 - o Initiation of immune tolerance induction (ITI)
 - o First negative inhibitor test during ITI
 - First normal recovery during ITI
 - o Confirmed inhibitor relapse after a successful ITI procedure (if positive, the

aforementioned information is also collected for the second inhibitor)

Determinants and outcomes calculated from collected data are:

• Clinical bleeding phenotype

Our score for bleeding severity is based on the bleeding severity score by Schulman et al. [97] Schulman et al also includes a joint subscore, however, we do not have this data for all patients, therefore we have decided to remove the joint subscore from the final score. Our bleeding severity score consists of 2 components; the annual joint bleed rate and annual factor consumption (corrected for bodyweight). Lastly, we will calculate the annual joint bleed rate/factor consumption using information from the HiN-6 questionnaire:

We will obtain the patient-reported annual joint bleed rate for the year 2016 using the HiN-6 questionnaire. This value is divided by 20 (which the roughly equal to the maximum number of joint bleeds that a patient without any treatment will experience). [97] This gives you a value between 0 and 1. We will obtain the patient-reported annual factor consumption for the year 2016 using the HiN-6 questionnaire. This number is divided by the mean body weight of the patient during this period. This value is then divided by 6000 (IU / kg), which is approximately the maximum consumption of regular prophylaxis. [97] This gives you a value between 0 and 1. The final score is simply the sum of the two aforementioned subscores, the score has a minimum of 0 and a maximum of 2.

• **BMI:** BMI is calculated as weight (kg) divided by height² (meters).

Chapter 6 – Substudies

This chapter describes all substudies that will be performed as part of the HiN-6 project. The objectives of the substudies are derived from the following overarching general objectives:

- 1. Describing the health status of the Dutch haemophilia population
- 2. Assessing the quality of life of PWH in the Netherlands
- 3. Assessing the quality of care of PWH in the Netherlands

- 4. Elucidating the variability in clinical phenotype among PWH
- 5. Assessing immunological mechanisms that may lead to inhibitor formation in patients with haemophilia A

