HiN-6	Haemophilia in the Netherlands 6

HJHS	Haemophilia joint health score
HRQoL	Health-related quality of life
HSES	Haemophilia-specific self-efficacy scale
iCHEC	Identifying children with hereditary coagulation disorders (paediatric bleeding
	assessment tool)
ICMJE	International Committee of Medical Journal Editors
IFNγ	Interferon gamma
lgA, lgG, lgM	Immunoglobulin A, G, M
IL-10	Interleukin-10
ITI	Immune tolerance induction therapy, frequent administration of relatively high
	doses of FVIII with the aim of eradicating inhibitors.
LPS	Lipopolysaccharide
LUMC	Leiden University Medical Centre
METC	Medical research ethics committee (MREC); in Dutch: Medisch Ethische
	Toetsingscommissie (METC)
MHCII	Major histocompatibility complex II
MoDC	Monocyte-derived dendritic cell
MUMC	Maastricht University Medical Centre
NHA	Nijmegen Haemostasis assay
NNA	Non-neutralizing antibodies
NVHP	Dutch Association of Haemophilia Patients (in Dutch: Nederlandse Vereniging van
	Hemofiliepatiënten)
PAM-13	Patient Activation Measure (questionnaire)
PBMC	Peripheral blood mononuclear cells
PCR	Polymerase chain reaction
PedHAL	Paediatric Haemophilia Activities List
РК	Pharmacokinetics
РТ	Prothrombin time
PUP	Previously untreated patient
PWH	Person with haemophilia
QoL	Quality of Life
Radboud UMC	Radboud University Medical Centre
RAND-36	Research and development 36-item health survey
VWF:Rco	Von Willebrand factor Ristocetin cofactor assay

RNA	Ribonucleic acid			
Sponsor	The sponsor is the party that commissions the organisation or performance of the			
	research, for example a pharmaceutical company, academic hospital, scientific			
	organisation or investigator. A party that provides funding for a study but does not			
	commission it is not regarded as the sponsor, but referred to as a subsidising party.			
SVR	Sustained viral response			
TAFI	Thrombin activatable fibrinolysis inhibitor			
TF	Tissue factor			
TGF-beta	Transforming growth factor beta			
TLR-ligand	Toll-like receptor ligand			
τΝFα	Tumour necrosis factor alpha			
Tregs	Regulatory T-cells			
UMCG	University Medical Centre Groningen			
UMCU	University Medical Centre Utrecht			
VERITAS-	Validated Haemophilia Regimen Treatment Adherence Scale Prophylaxis / On-			
pro/prn	Demand			
VWD	Von Willebrand disease			
VWF	Von Willebrand Factor			
VWS	Ministry of Health, Welfare and Sport			
WHO	World Health Organization			
Wbp	Personal Data Protection Act (in Dutch: Wet Bescherming Persoonsgevens)			

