Determinants: The following parameters of the CAT assay will be used as determinants; lag-time, time to peak, peak height and endogenous thrombin potential. FVIII concentration (measured using the chromogenic assay) will also be used as a determinant.

Endpoint: The modified bleeding severity score developed by Schulman et al [97] will be applied to this study population (see paragraph 5.1.3) and used as a dichotomous outcome. Mild bleeders will be defined as being in the lowest two quartiles of the modified bleeding severity score, severe bleeders will be defined as being in the highest two quartiles of the modified bleeding severity score. **Statistical analysis:** The CAT assay parameters and FVIII concentration will be used to predict if a patient is a mild or a severe bleeder (based on the modified bleeding severity score). We will quantify diagnostic performance by constructing ROC-curves for each parameter of the CAT assay

and for FVIII concentration. We will then test if the AUROC of each parameter of the CAT assay differs significantly from the AUROC of the chromogenic assay. This analysis will be performed for the total population and separately for each category of severity.

6.4.2 To assess the usefulness of the Nijmegen Haemostasis Assay (NHA) in relation to clinical phenotype:

Primary objective 1: To assess the association between the results of the NHA and the self-reported clinical bleeding phenotype of patients with severe, moderate and mild haemophilia A and B.
Study design and population: A cross-sectional study design will be used. The population will consist of all haemophilia A and B patients in the Netherlands.

Determinant: The following parameters of the NHA will be used as determinants; lag-time, thrombin peak-time, thrombin peak-height, area under the curve (AUC), fibrin lysis time (FLT), plasmin peak-height and plasmin potential.

Potential confounders: FVIII/FIX genotype, VWF antigen levels and VWF activity.

Endpoint: The modified bleeding severity score developed by Schulman et al [97] will be used as the endpoint (see paragraph 5.1.3). **Statistical analysis:** The association between each parameter of the NHA and bleeding severity will be assessed using linear regression.

Primary objective 2: To evaluate if the NHA can accurately diagnose the self-reported clinical bleeding phenotype of patients with severe, moderate and mild haemophilia.

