2.2: (definition of joint bleed)

• Joint bleeds are defined as complaints in ankles, knees, elbows, hips, wrists, or shoulders requiring treatment with FVIII at least once.

2.3 (information about prophylaxis and on-demand treatment):

- Prophylaxis is the regular infusion of clotting factor concentrates to prevent bleeding. Patients who are not on prophylaxis are treated "on demand", i.e. treatment is only given at the time of a bleed to make it stop.
- Some patients can be treated with prophylaxis to prevent bleeds AND immune tolerance induction (ITI) to treat inhibitors. Information on ITI is reported separately (see 3.3).

3.0 (additional information)

• Only proceed with chapter 3.0 if the patient has haemophilia A, if the patient has haemophilia B, proceed to chapter 4.0.

3.1 (definition of inhibitor development):

• Inhibitor development is defined as the occurrence of neutralizing antibodies against FVIII as measured with the Bethesda assay.

3.2-3.3 (information about ITI)

- Immune tolerance induction (ITI) is used to treat patients with FVIII inhibitors.
- ITI involves the repeated administration of FVIII concentrates over a period of weeks to years, with the goal of inducing antigen-specific tolerance.
- Some patients are also administered immunosuppressive drugs to increase ITI success.

3.4-3.16 (additional information about inhibitor development):

- For inhibitors to be considered relevant, they should be documented on two separate occasions within a 1-4 week period and should have a level of ≥ 0.6 Bethesda units (BU) per mL.
- For inhibitors to be considered clinically significant, they should be associated with < 66% recovery of the particular product on a blood sample obtained 10–15 min after completion of the factor infusion
- An exposure day (ED) is defined as a calendar day during which one or more infusions of factor VIII or FIX were given.

3.10 (information about inhibitor relapse)

• Relapse of an inhibitor was defined as the recurrence of the inhibitor upon rechallenge with FVIII after prior inhibitor disappearance.

4.4 (definition of sustained virologic response)

- Sustained virologic response (SVR) is defined by the absence of HCV RNA by polymerase chain reaction 12 weeks after stopping treatment.
- An SVR is associated with a 99 percent chance of being HCV RNA negative during long-term follow-up and can therefore be considered as being cured of the HCV infection.

Aŗ	Appendix 2: Sample collection form				

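### The consumption half of the bleeding severity score counts factor given for immune tolerance induction as bleeding severity, and no written cap keeps it within its stated range

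*Protocol*

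**What the plan says.** Protocol section 5.1.3 (clinical bleeding phenotype) builds the modified score from two parts: "Our bleeding severity score consists of 2 components; the annual joint bleed rate and annual factor consumption (corrected for bodyweight").

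- **Bleeds.** The self-reported joint bleeds of 2016 are scaled: "This value is divided by 20 (which the roughly equal to the maximum number of joint bleeds that a patient without any treatment will experience").
- **Consumption.** "We will obtain the patient-reported annual factor consumption for the year 2016 using the HiN-6 questionnaire" The amount is divided by body weight, and then: "This value is then divided by 6000 (IU / kg), which is approximately the maximum consumption of regular prophylaxis".
- **Range.** Each part is said to lie between 0 and 1. For the sum: "The final score is simply the sum of the two aforementioned subscores, the score has a minimum of 0 and a maximum of 2".

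The section neither limits consumption by indication nor says what happens above 6000 IU/kg.

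The list of abbreviations defines ITI as frequent, relatively high "doses of FVIII with the aim of eradicating inhibitors". The CRF instruction sheet (Appendix 1, item 2.3) keeps it apart from prophylaxis: "Some patients can be treated with prophylaxis to prevent bleeds AND immune tolerance induction (ITI) to treat inhibitors".

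The score is the endpoint of the CAT analyses (6.4.1), the NHA analyses (6.4.2) and the analysis of non-neutralizing antibodies and bleeding (6.5.1, secondary objective 3). It is used as a continuous outcome in linear regression. In the CAT and NHA diagnostic analyses it is split in the middle into mild and severe bleeders. For the NHA: "The population will consist of all haemophilia A and B patients in the Netherlands". Neither the CAT nor the NHA population excludes patients on ITI. Section 6.5.1 excludes patients with inhibitors, but not a patient on ITI whose inhibitor test has turned negative.

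**The concern.** Numerator and divisor do not match. The divisor is the ceiling of regular prophylaxis, while the numerator is all factor used. ITI is factor by definition, and its stated purpose is not to prevent or treat bleeds. The protocol recognises the distinction on the CRF, but the score draws on the questionnaire total and makes no use of it.

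Two things follow. First, a bleed-free patient can be placed in the severe half of the score because of inhibitor eradication. Second, since the stated 0 to 1 and 0 to 2 ranges are asserted and not enforced, such a patient can lie well outside them and carry undue weight in the linear regressions. The CAT and NHA parameters would then be judged against a phenotype that is partly a record of ITI.

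**Working it through.** **The plan's own range.** Score = joint bleeds/20 + (IU/kg per year)/6000. With 0 bleeds and 0 IU/kg it is 0; with 20 bleeds and 6000 IU/kg it is 1 + 1 = 2. The stated range is reproduced, but only while consumption stays at or below 6000 IU/kg and bleeds at or below 20.

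**Exchange rate.** 6000/20 = 300 IU/kg counts as one joint bleed. The consumption part passes 1 once average use over the year exceeds 6000/365 = 16.4 IU/kg per day. A bleed-free patient passes 2 above 12000 IU/kg, or 32.9 per day.

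**ITI, no bleeds.** The protocol gives no ITI amounts. The inputs below are assumptions for arithmetic only and say nothing about dosing.

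| Assumed use | IU/kg in the year | Score | Joint-bleed equivalent |
|---|---|---|---|
| 25 IU/kg every other day, 3 months | 1141 | 0.19 | 3.8 |
| 25 IU/kg every other day, full year | 4563 | 0.76 | 15 |
| 50 IU/kg three times a week, full year | 7800 | 1.30 | 26 |
| 50 IU/kg daily, full year | 18250 | 3.04 | 61 |
| 100 IU/kg daily, full year | 36500 | 6.08 | 122 |
| 200 IU/kg daily, full year | 73000 | 12.2 | 243 |

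**Median split.** The cut depends on a case mix that the protocol does not give. I assumed cohorts with 30 to 50% severe, 15% moderate and the rest mild; prophylaxis in 80% of severe and 25% of moderate patients, at 1500 to 6000 IU/kg per year. The medians were 0.00 to 0.13 overall and about 0.63 (severe), 0.07 (moderate) and 0.00 (mild). On these figures every row of the table lies above the overall median. Within the severe stratum, the full-year rows lie above the median and the 3-month row (0.19) does not.

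**Linear regression.** Assumed: n = 1000, residual SD 0.35, mean score m = 0.5, and a standardised assay parameter with its slope set for 80% power, b = (1.96 + 0.84) × 0.35/√1000 = 0.031. Suppose k patients have score c regardless of the assay. Then

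- variance = 0.35²(1 − k/n) + (k/n)(1 − k/n)(c − m)²
- power = Φ[b(1 − k/n)√n/√variance − 1.96]

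For k = 5 and c = 3: variance = 0.1219 + 0.004975 × 6.25 = 0.153, SD 0.391, power 0.70.

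| Score c | k = 1 | k = 5 | k = 10 |
|---|---|---|---|
| 1 (bleed-free, stated range enforced) | 80% | 79% | 79% |
| 2 | 79% | 76% | 73% |
| 3 | 78% | 70% | 62% |
| 6 | 71% | 46% | 32% |

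Simulation of the m = 0.5 cases agreed to within two percentage points. With m between 0.2 and 0.6, the k = 5 results at scores 3 and 6 are 68 to 71% and 44 to 47%.

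**Planned surgery.** No amount is given. An assumed 100 to 1500 IU/kg adds 0.02 to 0.25 (0.3 to 5 joint bleeds). That can cross the median in mild patients and sometimes in moderate ones, but one operation alone would not do so among severe patients.

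**The case against.** **The stated maximum is 2.** If the sponsor intends the range to bind, a bleed-free patient on ITI scores at most 1.0, the same as full regular prophylaxis, and the power loss is negligible. This stands as to size. The binding rule is not written, however, and a cap would leave ITI counted as bleeding.

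**Few such patients may be analysed.** Section 5.1.2 makes blood sampling voluntary and requires at least 3 days since the last FVIII. A patient on daily ITI at sampling could not be included without a break in dosing. This stands. Patients whose ITI fell in 2016 and ended before sampling remain. The CAT substudy has only 75 patients and may contain none.

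**The median split ignores outlier size.** Correct: in the ROC and logistic analyses only the side of the cut matters. A severe patient would often be above the overall median through prophylaxis alone, so reclassification matters most in the CAT analyses within severity class.

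**Prophylaxis without bleeds also scores about 1.0.** True, but that is part of the score by design and the divisor is scaled to it.

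**The questionnaire is a separate document and may split use by reason.** Possibly, but section 5.1.3 uses no such split.

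A reader might go further and infer that bleed-free patients on ITI or with surgery will be scored as severe bleeders, or that power will certainly fall sharply. The documents support neither. The first depends on amount, duration and stratum. The second needs an uncapped score and a number of patients that the protocol does not give. Nor is surgery as clear a case as ITI: joint replacement can follow blood-induced joint damage, which the introduction treats as a consequence of the disease, so this factor use is not plainly unrelated to phenotype.

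**Conclusion.** The point holds for ITI. As written, the consumption part counts factor whose stated purpose is inhibitor eradication, at 300 IU/kg per joint bleed, and does so in CAT and NHA populations that do not exclude these patients. A patient who did not bleed can be classed as a severe bleeder. Because no cap is written, the score can also exceed its stated maximum of 2. The definition and its range are fixed in the protocol itself, so this is not detail left for a later plan.

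The exchange rate and the thresholds for leaving the range rest on the protocol's divisors alone. The scores under ITI, the medians and the power figures rest on the assumptions shown. With the range enforced, the effect on the regressions is about one percentage point of power. Without it, the effect runs from 2 points (one patient scoring 3) to 48 points (ten scoring 6). Surgery warrants a sensitivity analysis and no more. The correction is worth making because it is cheap and concerns the endpoint of several analyses.

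**What to change.** 1. In section 5.1.3, define the consumption part as factor given as regular prophylaxis plus factor given to treat bleeds.
2. Identify patients with ITI during 2016 from CRF items 3.2, 3.7 and 3.14 and the inhibitor section of the questionnaire. Item 3.2 alone is not enough: it records only ITI under way when the form is completed, and the CRF has no field for the date on which ITI stopped.
3. Leave out of the score-based analyses those whose ITI use cannot be separated, and report how many.
4. Either write a cap for each part or correct the stated 0 to 1 and 0 to 2 ranges.
5. As sensitivity analyses, report the score on total consumption, and the results without patients who had planned surgery in 2016 (from the hospital admissions section).

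Cost: a change of wording, some linkage of CRF and questionnaire data, and the loss of a few patients from the score-based analyses.

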6.1 Studies describing the health status of the Dutch haemophilia population

6.1.1 45 years of haemophilia treatment in the Netherlands, 1972-2017

Primary objective 1: To describe changes in bleeding, factor consumption, self-reported bleedinginduced joint damage, inhibitor formation, HIV/HCV infection as well as cause-specific and all-cause mortality among Dutch PWH for the period 1972-2017.

Study design and population: We will compare between HiN-study cohorts (previous and current) on the endpoints stated below. For mortality, we will also compare our data to that of the general male population. The population will consist of all previous HiN-study cohorts as well as the current HiN-6 cohort.

Determinant: Disease severity and calendar time

Endpoints: Self-reported annual joint bleed rate/factor consumption, self-reported bleeding-induced joint disease, inhibitor formation, HIV/HCV infection, all-cause/cause-specific mortality will be used as endpoints. Information on these endpoints will be obtained using a questionnaire. **Statistical analysis:** We will use descriptive statistics where appropriate.

Primary objective 2: To describe the prevalence of several haemophilia-related and nonhaemophilia related co-morbidities in the Dutch haemophilia population and to compare these results with the general Dutch male population.

Study design and population: A cross-sectional study design will be used. The population will consist of all PWH in the Netherlands.

Determinant: Disease severity, HIV/HCV infection status and inhibitor status.

Endpoints: Cardiovascular disease (CVD), malignancies, obesity, liver disease, chronic kidney disease (CKD), diabetes, osteoporosis, chronic pain and mental health. Information on these endpoints will be collected using a questionnaire and/or from each patient's medical record.

Statistical analysis: We will use descriptive statistics, standardized by age. Our results will be compared with national figures for the general male population provided by the Central Bureau of Statistics Netherlands StatLine databank, standardized directly or indirectly by age.

HiN-6 study

Primary objective 3: To describe the uptake, efficacy and safety of hepatitis C treatment in PWH currently or previously infected with hepatitis C.

Study design and population: A cross-sectional study design will be used. The population will consist of all PWH in the Netherlands currently or previously infected with hepatitis C. **Determinant:** Last treatment for hepatitis C will be used as the determinant. Treatment type is subdivided into never treated for hepatitis C, treated with direct-acting antivirals only, treated with direct acting antivirals + ribavirin or treated with (peg)interferon + ribavirin.

Potential confounder: HCV genotype

Endpoint: Uptake, efficacy and safety will be used as the endpoints. Uptake is defined as the proportion of patients that were treated with a given treatment type. Efficacy is defined as achieving a sustained viral response (SVR), which is defined as the absence of detectable RNA of the hepatitis C virus in blood serum for at least 24 weeks after discontinuing treatment. Safety-endpoints are defined as having had any of the following adverse-effects during treatment with antiviral therapy; Headache, fatigue, concentration problems, insomnia, depressive symptoms, anxiety, irritability, flulike symptoms, nausea, diarrhoea, pruritus, asthenia, dyspnoea, arthralgia, myalgia, rash, cachexia or jaundice.

Statistical analysis: We will describe the uptake, efficacy and safety of the different hepatitis C treatment types using descriptive statistics.

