4.3 Previous HCV treatment			
regimens? (max. 6 options)	Start date of first treatme	nt:	_dd/mm/yyyy
	Treatment regimen (multi	ple choice):	
	Interferon	Pegylated	l interferon
		🗆 Unknown	
	Direct acting antivirals:		
	Start date of second treat	ment:	dd/mm/yyyy
	Treatment regimen (multi		
			l interferon
	🗆 Ribavarin	 Pegylated Unknown 	1
	Direct acting antivirals:		
	Start date of third treatme	ent:	_dd/mm/yyyy
	Treatment regimen (multi		
	Interferon	 Pegylated Unknown 	l interferon
	🗆 Ribavarin	🗆 Unknown	1
	Direct acting antivirals:		
	Start date of fourth treatm		_dd/mm/yyyy
	Treatment regimen (multi		
	Interferon	Pegylated	l interferon
		🗆 Unknown	
	Direct acting antivirals:		
	Start date of fifth treatme		_dd/mm/yyyy
	Treatment regimen (multi		
	Interferon	 Pegylated Unknown 	l interferon
	Direct acting antivirals:		
	Start date of sixth treatme	ent:	dd/mm/yyyy
	Treatment regimen (multi	ple choice):	
	Interferon	Pegylated	l interferon
	🗆 Ribavarin	🗆 Unknown	1
	Direct acting antivirals:		
4.4 sustained virologic response	O patient is still undergoin	ig treatment	
(SVR) after last HCV treatment?	O Unknown		
	O No		
	O Yes, date:		_dd/mm/yyyy

Instruction sheet Case Report Form HiN-6/Parel Hemofilie

1.1 (primary cause of death)

- Report the primary (underlying) cause of death. The primary cause of death is defined as the disease or event that started the chain of events that led to death.
- After completion of the study, this information will be recoded according to the ICD-10 classification system.

1.5 (reporting F8 or F9 genotype)

- In case of point mutation, please provide both nucleotide and amino acid change
- Please provide whether numbering is given according to HAMSTeRS/HADB nomenclature ('old' numbering) or HGVS nomenclature ('new' numbering).

1.6-1.11 (FVIII and VWF assays)

- Report the results of the LAST assay that was performed.
- Convert assay results to IU/mL if they were reported differently (e.g IU/dL) in the EPD.

1.10 (baseline Von Willebrand activity)

• If a VWF:Rco assay (the main VWF activity assay) was never performed but another type of VWF activity assay was used, report the results of that assay instead.

1.12-1.14 (additional bleeding disorders)

• If mentioned in the EPD, report any additional bleeding disorder that the patient may have.

2.1 (definition of exposure day):

• An exposure day (ED) is defined as a calendar day during which one or more infusions of factor VIII or FIX were given.

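### Grouping hepatitis C patients by last treatment biases the interferon SVR upward if any interferon failure switched class; two classes are missing and SVR has two definitions

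*Protocol*

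**What the plan says.** The design is in Protocol section 6.1.1, primary objective 3.

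- **Population:** "The population will consist of all PWH in the Netherlands currently or previously infected with hepatitis C".
- **Grouping:** "Last treatment for hepatitis C will be used as the determinant". The classes begin: "Treatment type is subdivided into never treated for hepatitis C, treated with direct-acting antivirals only". The other two are direct-acting antivirals with ribavirin, and (peg)interferon with ribavirin.
- **Uptake:** the share of patients given a treatment type. The text does not say whether this means ever or last.
- **Efficacy:** SVR, defined as "absence of detectable RNA of the hepatitis C virus in blood serum for at least 24 weeks after discontinuing treatment".
- **Analysis:** descriptive, by treatment type.

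The data come from section 5.1.3 and the CRF in Appendix 1. Item 4.3 records up to six successive courses, each with a start date and multiple-choice boxes for interferon, pegylated interferon, ribavirin and direct-acting antivirals. It has no stop date. Item 4.4 asks for SVR after the last treatment only, with a date if the answer is yes. The instruction sheet for item 4.4 reads: "Sustained virologic response (SVR) is defined by the absence of HCV RNA by polymerase chain reaction 12 weeks after stopping treatment".

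**The concern.** Whether a regimen is a patient's last depends on whether it worked. Success usually ends treatment, and failure may lead to another regimen. Grouping by last regimen therefore groups partly by outcome, and the interferon row is selected for success. Describing efficacy by treatment type is the whole content of this primary objective, so a grouping rule that shifts one row spoils the comparison a reader will make.

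Two further defects touch the same table. Some recordable regimens have no row. The endpoint also has one definition for the analyst and another for the person reading the charts.

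**Working it through.** **Plan's own figure.** The protocol gives no SVR rate, number of infected patients or re-treatment rate for this objective. Its only sample-size figure, 1800 × 0.70 = 1260 participants (section 4.4), reproduces but has no bearing here.

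**Step 1: who leaves the interferon row.** Take patients ever treated with (peg)interferon plus ribavirin.

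- Let p be the share who reach SVR on that class (assumed).
- Let r be the share of those who do not reach it and later receive a different class (assumed).
- Those cured stay in the row: p.
- Failures who did not switch class stay: (1 − p)(1 − r). This includes patients re-treated only with another interferon–ribavirin course, because section 6.1.1 pools them in one class.
- Failures who switched class leave: (1 − p)r.

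The SVR shown under the last-treatment rule is

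p / [p + (1 − p)(1 − r)].

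The denominator equals 1 − (1 − p)r. This is below 1 whenever r > 0 and p < 1, so the result then exceeds p for any p > 0. It equals p when r = 0.

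**Step 2: illustration.** With p = 0.50 and r = 0.50, of 100 patients 50 are cured, 25 failures stay and 25 leave. The row shows 50/75 = 66.7% instead of 50%. Over a range of assumed values:

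| Assumed p | r = 0.25 | r = 0.50 | r = 0.75 |
|---|---|---|---|
| 30% | 36.4% | 46.2% | 63.2% |
| 40% | 47.1% | 57.1% | 72.7% |
| 50% | 57.1% | 66.7% | 80.0% |
| 60% | 66.7% | 75.0% | 85.7% |

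**Step 3: uptake.** If uptake is counted by last treatment, the interferon count loses (1 − p)r of its ever-users. That is 25% at p = r = 0.50, and 17.5% at p = 0.30, r = 0.25.

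**Step 4: classes.** Compare the boxes on CRF 4.3 with the four classes in section 6.1.1. Interferon (plain or pegylated) without ribavirin can be ticked but has no class. The same holds for interferon together with a direct-acting antiviral.

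**Step 5: SVR time point.** Section 6.1.1 requires undetectable virus "for at least 24 weeks after discontinuing treatment". The CRF instruction accepts "absence of HCV RNA by polymerase chain reaction 12 weeks after stopping treatment". A patient with between 12 and just under 24 weeks of negative follow-up is a yes on the CRF but does not yet meet section 6.1.1.

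Without a stop date, the time off treatment cannot be calculated. The SVR date minus the start date of the last course gives an upper limit for it. If that limit is under 24 weeks, the 24-week definition cannot be met. If it is longer, the question stays open. The check is therefore partial.

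**The case against.** **The bias needs a switch of class, and its size is unknown.** A reader might infer that every re-treated interferon failure drops out of the interferon group. Re-treatment within the pooled interferon–ribavirin class leaves the patient where he was, so only switches to another class matter. A reader might also take the larger table entries as estimates. Neither p nor r is in the documents, so the entries show direction and scale only. Both limits stand. The direction does not depend on them.

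**The SVR conflict is not tied to one treatment.** It is tempting to say that the 12- versus 24-week difference falls mainly on patients given direct-acting antivirals. The documents give no calendar timing or numbers by regimen, so this cannot be said. Nor is the interval wholly uncheckable, as step 5 shows.

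**Uptake may already mean ever treated.** The definition can be read that way, and all previous regimens are collected. The undercount is therefore conditional on the other reading.

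**The treatment course is not the right replacement unit.** It would change the question from patients to courses. With assumed figures, suppose 40 of 100 patients are cured by a first interferon course, 30 of the 60 failures receive a second, and 9 of those are cured. The patient-level rate is 49/100 = 49%; the course-level rate is 49/130 = 38%. With no switch of class, the last-treatment rule already gives the correct 49%. Course-level reporting would also need reinfection and side-effect fields that the CRF lacks. This objection stands and shapes the fix.

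**The objective is only descriptive.** No test or sample size depends on it, and the regimen history allows regrouping at analysis. That limits the consequence, but section 6.1.1 itself fixes the grouping and nothing in the protocol corrects it. The full questionnaire is a separate document that is not shown and may ask for outcomes per course. That would not change the stated grouping rule or the two SVR definitions.

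**Conclusion.** The point holds as bias in a descriptive estimate; no formal test is affected. Classifying by last treatment overstates the interferon SVR whenever at least one interferon failure was later given a different class. The bias is zero only if there was no such switch. The six course slots on CRF 4.3 show that the plan allows for successive treatments, but they do not show how many patients switched. The illustration of 50% shown as 67% rests wholly on assumed values.

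The two missing classes and the conflict between 24 and 12 weeks need no assumption: both follow from current text set side by side. Which time point should apply is not for this review to say.

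**What to change.** 1. **Efficacy and uptake.** In section 6.1.1, replace the last-treatment grouping with a per-patient, ever-treated denominator for each class, built from CRF 4.3. Count a class as no SVR when it was followed by a switch to another class, and use CRF 4.4 for the patient's last class. State the assumption that re-treatment was not for reinfection. A patient can then appear in more than one row, so the rows will not add up to the number of patients; say so in the table.
2. **Last-treatment table.** Keep one only if it is labelled as such.
3. **Classes.** Add interferon alone and interferon plus a direct-acting antiviral.
4. **SVR.** Reconcile the time point between section 6.1.1 and the CRF instruction for item 4.4.
5. **Optional.** Add a stop date for the last course, so that the interval can be verified.

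The cost is protocol and CRF wording and slightly more analysis work; items 1 to 4 need no new data field. The interferon SVR will look less favourable if any switches occurred. The optional stop date adds a little chart abstraction.
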